2.1 Study variables

2.1.1 Demographic and baseline characteristics

Demographic assessments (age, gender, ethnicity, height and weight) are performed at the screening visit. Body Mass Index (BMI) will be derived from the height and weight entered, as follows:

$$\text{BMI} = \text{weight (kg)} / \text{height (m}^2\text{)}$$

Medical history items are also recorded at the screening visit using a defined list of conditions and recorded as never, past, or present. No derivation of data based on medical history will be undertaken.

A full physical examination is performed at the screening visit. No derivation of data based on physical examination findings will be undertaken.

Risk factors recorded at the screening visit will be collected. No derivation of risk factors will be undertaken.

For lymphatic surgery, lymphedema stage will be reported.

2.1.2 Operative variables

There are three types of procedure: free flap, replantation, and lymphatic procedures. A patient may have more than one type of procedure within the same operation. For each type of procedure, the relevant CRF forms will be completed.

The Dendrite eCRF forms for different types of procedure will be 'grouped' together into operations if the date of the operation recorded on form E is the same.

The Castor eCRF forms are grouped into the following options: Free Flap Procedure, Replantation Procedure, Lymphatic Procedure or Free Flap and Lymphatic Procedure. For patients who undergo both free flap and lymphatic procedures, they will be entered under the same participant ID.

For each type of procedure in Dendrite, the time of entering the operating room (OR) and leaving the OR is recorded on form E (patient in, patient out).

For each type of procedure in Castor, the time of entering the operating room (OR) and leaving the OR is recorded as follows:

Free Flap Operation Visit: Operation Data Form

Replantation Operation Visit: Replantation Operation Form

LVA Operation Visit: LVA Operation Form

Sponsor: MMI Product: Symani system for microsurgical anastomosis Study: PRIMO	
Statistical Analysis Plan Final 22 November 2024	

This will be checked for consistency across different forms within the one operation since all types of procedure on the same day would be expected to be the same visit to the OR, so the same time of entering and leaving OR.

For each operation, the total time in OR will be derived using data on Dendrite's form D, or Castor's procedure specific visit, Operation Form as:

$$\text{OR time (mins)} = \text{Patient out} - \text{patient in.}$$

For each type of procedure, the incision start time and closure end time are recorded. The operative time will be derived as:

$$\text{Operative time (mins)} = \text{closure time} - \text{incision time.}$$

Note, this may be different for each type of operation conducted within the one operation (i.e. within one visit to OR).

Use of venous thromboembolism (VTE) prophylaxis, antibiotics, anticoagulants, and inotropes during the procedure is recorded using checkboxes. No derivations will be made.

Donor site

The donor site, side, type of tissue transfer (pedicled or free) and composition are recorded using checkboxes. No derivations will be made. In addition, the flap name is recorded using a numerical code. This is grouped by location (head and neck, trunk front, trunk back, upper limb, lower limb) and within location a name. The codes will be used to assign the location.

The requirement for a re-operation (at the donor site) is recorded. If a re-operation is required, the date and type of re-operation (collected using tick boxes) is recorded. Re-operation is a specific secondary endpoint, see below.

The time (in days) from initial operation to re-operation will be derived as:

$$\text{Date of donor site re-operation} - \text{date of initial operation} + 1 \text{ days.}$$

Free flap ischemia time is recorded.

Recipient site (free flaps)

Recipient site is grouped within the eCRF as:

- Head and neck
- Trunk
- Perineum
- Upper limb
- Lower limb
- Breast

Sponsor: MMI Product: Symani system for microsurgical anastomosis Study: PRIMO	
Statistical Analysis Plan Final 22 November 2024	

For analysis, this will be collapsed into 4 categories; namely head and neck, extremities (upper and lower limb), breast and other (includes trunk and perineum).

For the recipient site, for each overall location (i.e. head and neck, trunk, perineum, upper limb, lower limb, breast) further details of location are collected using tick boxes.

In addition, details are recorded for the recipient arteries and veins (i.e. which vessels are involved), the reason for surgery (i.e. recipient indication), exposed anatomy, infection indications and tumor type are all recorded using tick boxes. No derivations are planned.

For all recipient locations, the requirement for re-operation is collected. If a re-operation is required, the date and type of re-operation (collected using tick boxes) is recorded. The side is also recorded. Re-operation is a specific secondary endpoint, see below.

The time (in days) from initial operation to re-operation will be derived as:

Date of recipient site re-operation – date of initial operation +1 days.

No further derivations will be made.

Lymphedema location (lymphatic surgery).

The lymphedema location is collected ((11 options). These will be combined for analysis as follows:

- Head and neck will include head, neck and face
- Upper limbs will include hand, forearm, arm, upper arm
- Lower limbs will include – foot, leg, thigh, calf.

Replantations

Replantations can be free flap or nerve.

In addition, recipient site has the same options as free flaps and will be collapsed into 4 categories as defined above for free flaps.

Anastomosis

Information is collected for each anastomosis, including type of vessel (artery, accompanying vein, superficial vein, nerve lymphatic, other), type of anastomosis (end-to-end, end-to-side, vein graft or flow through), vessel diameter, pedicle length and suture size. No derivations will be made unless some categories are sparsely populated in which case categories may be combined for data summaries.

The intended operation (manual or robotic) is recorded together with the number of robotic sutures used and the number of manual sutures used. The robotic and manual execution time is recorded.

Total procedure execution time will be derived where possible.

Sponsor: MMI Product: Symani system for microsurgical anastomosis Study: PRIMO	
Statistical Analysis Plan Final 22 November 2024	

No further derivations will be made.

2.1.3 Effectiveness endpoints

Data collected from the operation(s) undertaken during the study will be used to define the effectiveness outcomes. As the timing of operations is important to assess the outcomes, the flow described in figure 2 will be used to assess the timing of procedures.

During the initial hospital stay, patients may undergo multiple operations as per standard of care. The date, start time, and end time of each operation will be recorded (Dendrite: form D, or Castor: Operation Form within procedure specific visit) and these will be used to sort the operations from earliest (index procedure) to latest. The date of discharge from hospital is recorded on Dendrite's form U1, or on Castor's Visit Forms (1-4). The time from the date of the index procedure to the date of discharge (inclusive) is defined as the perioperative period. Any operations recorded after the discharge date will be classified as a re-operation (after hospital re-admission).

Total hospital time (days) = peri-operative time = date of discharge – date of index procedure +1 (days).

2.1.3.1 Primary effectiveness endpoint – Procedure Robotic Success

Form R or Anastomosis Data Form will be completed for each anastomosis. If the answer to the question 'How did you intend to perform this anastomosis' is 'Robotic' then the anastomosis is included for this endpoint.

The endpoint will be derived for each anastomosis using the question "Did you experience any system technical issues resulting in unplanned return to conventional suturing".

If the response is 'No' and the number of robotic sutures is > 0 or the number of robotic redo sutures is > 0, the anastomosis will be classified as 'intra-operative change from robotic to manual' = 'no'.

If the response is 'yes' anastomosis will be classified as intra-operative change from robotic to manual = 'yes'.

If there is no response to the question the anastomosis classification will be missing.

If the planned approach was manual the result will be N/A

The unit of analysis for this endpoint is the anastomosis.

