Target Population and sample size	The patients selected for this PMCF activity will be adults (over 18 years) requiring microsurgical reconstructive procedures applied to arterial, venous, neural or lymphatic anastomosis. The planned minimum sample size is 402 patients to ensure lower 95% confidence limit for the Primary Endpoint. A drop out rate of 5% will allow to include a total of 420 subjects. All subjects will be enrolled and followed in at least 3 EU centres until the sample size is reached.

**RASM
POST MARKET CLINICAL FOLLOW-UP
STUDY
Synopsis**

CDC-00031
Rev. 03
Page: 2/4

Duration of Study	Each enrolled subject will be followed through the first 30±7 days post-operatively or 24 weeks post-operatively (according to the procedures) per the follow-up schedule reflecting the standard of care.
Primary Endpoint	The primary endpoint will be defined as the ability to complete the surgical task with Symani as intended by the surgeon. This endpoint will be referred to as “Procedure Robotic Success”.
Secondary Endpoints	
The main secondary endpoint will be the rating of the surgeon experience of robot usability, which will be assessed using a questionnaire.
 
Further secondary endpoints will be assessed regarding the clinical outcome of the procedures. These criteria will differ depending on the procedure performed being a replantation, free flap surgery, lymphatic surgery or other.
 
Replantations
 
• Time for each anastomosis execution and warm ischemia time (minutes)• Intraoperative need to redo the anastomosis (yes or no)• Postoperative need to redo within 7 days (complication and need to return to the operating room to explore anastomosis: yes or no)• Complications• Replantation Failure or Loss (subsequent amputation) 
Free Flaps
 
• Time for each anastomosis execution and warm ischemia time (minutes)• Intraoperative need to redo the anastomosis (yes or no)• Postoperative need to redo within 7 days (complication and need to return to the operating room to explore anastomosis: yes or no)• Complications• Flap Failure or Loss (yes or no) 
Lymphatic Surgery
 
• Time for each anastomosis execution (in minutes)• Intraoperative need to redo based on ICG Patency (yes or no)• Postoperative need to redo based on ICG Patency (yes or no)• Complications• Limb volume reduction

**RASM
POST MARKET CLINICAL FOLLOW-UP
STUDY
Synopsis**

CDC-00031

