1.3.1 Endpoints

Primary endpoint

The primary endpoint is defined as the ability to complete the surgical task with Symani as intended by the surgeon. This endpoint will be referred to as "Procedure Robotic Success".

Sponsor: MMI Product: Symani system for microsurgical anastomosis Study: PRIMO	
Statistical Analysis Plan Final 22 November 2024	

Secondary endpoints

The main secondary endpoint will be the rating of the surgeon's experience of robot usability, which will be assessed using the usability questionnaire.

Further secondary endpoints will be assessed regarding the clinical outcome of the procedures (e.g. time for each anastomosis). Some of these endpoints may differ depending on the procedure performed (replantation, free flap surgery, lymphatic surgery or other).

Replantation

- Time for each anastomosis execution or nerve coaptation
- Warm ischemia time (minutes)
- Intraoperative need to redo the anastomosis (yes or no)
- Postoperative need to redo within 7 days (Complication and need to return to the operating room to explore anastomosis: yes or no)
- Complications
- Replantation Failure or Loss (subsequent amputation)

Free Flaps

- Time for each anastomosis execution
- Warm ischemia time (minutes)
- Intraoperative need to redo the anastomosis (yes or no)
- Postoperative need to redo within 7 days (Complication and need to return to the operating room to explore anastomosis: yes or no)
- Complications
- Flap Failure or Loss (yes or no)

Lymphatic Surgery

- Time for each anastomosis execution (in minutes)
- Intraoperative need to redo based on ICG Patency (yes or no)
- Postoperative need to redo based on ICG Patency (yes or no)
- Complications
- Limb volume reduction

Sponsor: MMI Product: Symani system for microsurgical anastomosis Study: PRIMO	
Statistical Analysis Plan Final 22 November 2024	

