2.1.4 Questionnaires

For each patient, the surgeon will complete two questionnaires:

The exoscope/Symani questionnaire – this comprises 19 questions with a 5 point Likert scale response (Strongly disagree, disagree, neither agree nor disagree, agree and strongly agree), 5 questions with a binary response (yes/no) and 2 questions with a 5 point response (awful, negative, neutral, positive, fantastic).

In this questionnaire, all questions are phrased so that agree and strongly agree represent positive responses, as does 'positive' and 'fantastic'. In addition, for the binary responses all questions except 1, a 'yes' is a positive response. For the question "I needed to switch from robotic suturing to manual suturing because I was not comfortable with 3D vision", a 'No' is a positive response.

All questions will be classified accordingly as positive 'yes' or 'no'. The total number (and percentage) of positive responses will be derived.

If a question is not answered it will not be classified.

The usability questionnaire – this comprises 7 questions using a 5 point Likert scale (from strongly disagree to strong agree), one binary response question (yes/no), one question assessed on a scale of 1-10 and one question with 3 options (this question is used for the key secondary endpoint).

As above, all 5 point Likert scale questions 'agree' and strongly agree' represent a positive response.

Sponsor: MMI Product: Symani system for microsurgical anastomosis Study: PRIMO	
Statistical Analysis Plan Final 22 November 2024	

For the binary response question 'yes' is a positive response and for the scale of 1-10, a high number is a positive response. For classification of positive (yes/no) a value of ≥ 6 will be classified as positive.

For the 3 option question (the primary endpoint), responses of 'complete procedural success' and 'partial procedural success' will be classified as positive.

As for the exoscope questionnaire, the number (and percentage) of positive responses will be derived.

In addition, for each patient, the circulating nurse will complete a questionnaire with 6 questions on a 5 point Likert scale, one question on a 1-10 scale and the same question (as for the surgeon) rating the overall performance with 3 options.

As above, each question will be classified as positive (yes/no) and the number and percentage of positive responses derived.

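### The primary endpoint rule counts only returns to manual suturing caused by technical issues and gives zero-suture 'No' cases no category, so Procedure Robotic Success can be overstated

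*SAP*

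**What the plan says.** The protocol synopsis, under Primary Endpoint, states: "The primary endpoint will be defined as the ability to complete the surgical task with Symani as intended by the surgeon". SAP 1.3.1 repeats this: "The primary endpoint is defined as the ability to complete the surgical task with Symani as intended by the surgeon". Neither limits non-completion to equipment faults.

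SAP 2.1.3.1 takes each anastomosis with robotic intent and uses a single question: "Did you experience any system technical issues resulting in unplanned return to conventional suturing". Its branches are:

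- 'Yes': a change from robotic to manual occurred.
- 'No', "and the number of robotic sutures is > 0 or the number of robotic redo sutures is > 0": no change occurred.
- No response: missing.
- Planned manual: not applicable.

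SAP 2.4.4.1 then says that every anastomosis of a patient in the FAS is assigned Yes or No for robotic success, and refers back to 2.1.3.1. SAP 2.1.2 records the intended approach "together with the number of robotic sutures used and the number of manual sutures used", but the rule does not use the manual count. SAP 2.2.2.1 admits a patient to the FAS only if at least one anastomosis is classified as robotic, which normally means at least one robotic suture. SAP 1.7 sets the criterion: superiority to manual surgery is concluded if the lower 95% confidence limit exceeds 85%.

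**The concern.** The endpoint asks whether the task was completed with the robot as the surgeon intended. The rule asks whether a technical fault forced a return to hand suturing. The two differ whenever the surgeon switches for another reason, such as access, vessel quality or vision. The SAP foresees one such reason: a surgeon questionnaire item in 2.1.4 reads "I needed to switch from robotic suturing to manual suturing because I was not comfortable with 3D vision". That item does not feed the endpoint, and SAP 1.1 says the clinician questionnaires are unavailable for retrospective patients.

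The rate compared with 85% supports the study's only superiority statement. If non-technical switches are scored as success or left out of the denominator, the rate measures freedom from reported technical conversion, while the conclusion is worded as superiority to manual methods. SAP 1.5, which lists the changes from the protocol's statistical section, does not mention this narrowing.

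**Working it through.** **1. The rule applied case by case (robotic intent throughout)**

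| Answer | Robotic sutures, first attempt | Robotic redo sutures | Result under 2.1.3.1 | Task completed with Symani? |
|---|---|---|---|---|
| No | 1, then finished by hand for a non-technical reason | 0 | no change | No |
| No | 0 | 0 | no branch applies | No |
| No | 0 | 1 or more | no change | Not at first attempt |
| No | count missing | count missing | no branch applies, though 2.2.2.1 treats it as robotic | Unknown |
| Yes | any | any | change | No |

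The condition "the number of robotic sutures is > 0 or the number of robotic redo sutures is > 0" follows an 'and' without brackets. If the redo clause is read as standing alone, a 'Yes' answer with redo sutures meets two branches. Robotic redo sutures are not defined elsewhere in the SAP. The output variable is a change to manual. That 'no change' means success has to be inferred from the cross-reference in 2.4.4.1.

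The FAS condition acts in the same direction. A patient whose only robotic-intended anastomosis received no robotic suture is outside the FAS, even when the answer was 'Yes'.

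**2. The plan's own criterion**

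Inputs from SAP 1.7: n = 402, benchmark 85%, exact 95% limits. The Clopper-Pearson lower limit for x successes is the 2.5% quantile of Beta(x, n − x + 1). The smallest passing count is x = 356 (lower limit 85.03%). At a true rate of 85%, P(X ≥ 356) = 2.4%. At 89% it is 64.9%, against the 85% power stated in 1.7. That discrepancy is a separate matter and is not used here.

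**3. How many non-technical switches matter**

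Assumptions, not in the documents: 402 robotic-intended anastomoses, 24 technical conversions, m non-technical switches, and independence.

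- All switches count as failures: (378 − m)/402.
- SAP rule, each switch after at least one robotic suture: 378/402 = 94.0%, lower limit 91.2%, whatever m is.
- SAP rule, each switch a zero-suture 'No' that is dropped: (378 − m)/(402 − m).

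| m | All switches as failures (lower limit) | Zero-suture cases dropped (lower limit) |
|---|---|---|
| 10 | 368/402 = 91.5% (88.4%) | 368/392 = 93.9% (91.0%) |
| 20 | 358/402 = 89.1% (85.6%) | 358/382 = 93.7% (90.8%) |
| 22 | 356/402 = 88.6% (85.03%) | 356/380 = 93.7% (90.7%) |
| 23 | 355/402 = 88.3% (84.8%) | 355/379 = 93.7% (90.7%) |
| 40 | 338/402 = 84.1% (80.1%) | 338/362 = 93.4% (90.3%) |

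The conclusion changes at m = 23, which is 23/402 = 5.7%.

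**4. Chance of a superiority conclusion when the true as-intended rate is exactly 85%**

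Let k be the share of anastomoses switched for non-technical reasons (assumed). If these are scored as success, the apparent rate is 0.85 + k with n = 402. If they are dropped, it is 0.85/(1 − k) with n = 402(1 − k), rounded.

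| k | Scored as success | Dropped |
|---|---|---|
| 0% | 2.4% | 2.4% |
| 1% | 7.7% | 5.7% |
| 2% | 19.8% | 15.7% |
| 3% | 40.2% | 28.7% |
| 4% | 64.9% | 52.5% |
| 5% | 85.2% | 71.4% |

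**The case against.** The defence has five arguments.

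- **Completing as intended does not mean placing no manual suture.** SAP 2.1.2 and 2.1.3.2.2 record robotic and manual sutures and times for each anastomosis, so mixed suturing is foreseen and some of it may be planned. No field described in the SAP separates planned from unplanned manual sutures. This stands: zero manual sutures should not be the primary definition.
- **The SAP does not direct that zero-suture 'No' cases be excluded.** A reader might infer from 2.5.2 that it does. That section excludes outcomes with insufficient information, whereas 'No' with a recorded zero is complete information, and 2.4.4.1 promises a Yes or No. This stands in part: exclusion is a likely handling, not an instruction. The missing branch remains.
- **The questionnaire does not show that non-technical switches occur.** It shows only that one kind was foreseen, and some surgeons might report such a switch as a technical issue. This stands. The endpoint question does not ask for non-technical reasons, however.
- **Few switches may change nothing.** With 24 technical conversions, up to 22 further switches leave the conclusion intact. This stands, which is why a range is shown.
- **Mixed suturing will be visible elsewhere.** Anastomosis details (2.4.3), robotic and manual times (2.4.4.2.2) and questionnaire items (2.4.5) are tabulated. That is true, but none of them corrects the rate compared with 85%.

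Only the protocol synopsis is available here. The CRFs listed in SAP 1.4 are not, and they may hold a field the SAP does not describe.

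**Conclusion.** The derivation in 2.1.3.1 does not implement the endpoint defined in the protocol synopsis and SAP 1.3.1. It leaves out non-technical returns to manual suturing, lets redo sutures stand in for a first attempt with none, gives zero-suture 'No' cases no category, and never states the mapping to success. Each gap either raises the success rate or removes non-completions from it.

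The size is unknown, because the documents give no rate of non-technical switching. Under the assumed 24 technical conversions in 402, the criterion is affected only from 23 non-technical switches (5.7%). Near the benchmark the tolerance is smaller: at a true rate of 85%, a 2% share scored as success raises the chance of a superiority conclusion from 2.4% to 19.8%. These figures assume independent anastomoses and two-sided exact limits.

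A reader might infer that the superiority result must be false, or that the device would fail under a proper definition. The documents do not support that. They show that the rule cannot tell the two situations apart.

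**What to change.** Amend SAP 2.1.3.1 as follows:

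- State Success = Yes or No explicitly for every robotic-intended anastomosis.
- Score as No any with zero first-attempt robotic sutures, whatever the answer or redo count, and any with a return to manual suturing for any reason.
- Include robotic-intended anastomoses of patients who are outside the FAS only because no robotic suture was placed. The SAS in 2.2.3.1 already identifies attempted cases through a recorded robotic time.
- Because planned and unplanned manual sutures cannot be separated with the fields described, add a strict sensitivity analysis that counts any robotic-intended anastomosis with first-attempt manual sutures above zero as a failure.
- Base the superiority statement on a result that holds under that strict analysis. Otherwise limit the conclusion to freedom from technical-issue conversion.
- Keep the present rule as the separate approach-change endpoint in Appendix 1, which has no derivation of its own.
- List the change in SAP 1.5.

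The cost is SAP wording and derivation code, since intent and suture counts are already collected. If the CRFs hold no reason for a non-technical switch, mixed-suture cases may need clinical review, which 2.1.3.2.3 already uses for unmatched redo forms. The reported rate may be somewhat lower, and some planned hybrids will count as failures in the strict analysis.

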1. OVERVIEW AND INVESTIGATIONAL PLAN

1.1 Study design

The PRIMO study is a prospective, non-randomized, single arm, multicenter, post-market clinical follow-up (PMCF) study designed to evaluate the safety and effectiveness of the Symani System when used to assist microsurgical anastomoses in the real-world setting: i.e. it is a real world prospective observational data collection process. Patients selected will include adults (over 18 years) requiring microsurgical reconstructive procedures applied to arterial, venous, neural, or lymphatic anastomosis. Patients will be enrolled, undergo surgery, and have assessments made at regular intervals (day 1, day 4, day 14, day 30 (free flap), and 24 weeks (lymphatic anastomoses)).

An addendum to the PRIMO study was prepared and approved in December 2022. The addendum describes the addition of retrospective data collection to the PRIMO study. This will include patients with the same profile as the prospective data collected in the PRIMO study (i.e. ≥ 18 years requiring microsurgical reconstructive procedures applied to arterial, venous, neural, or lymphatic anastomosis) and will collect as much data as possible (based on availability) using the same data collection process as for the prospective data collection. Accordingly, the PRIMO study describes two data sources (prospective data collection and retrospective data collection), both collected under a common protocol. There will be some case report forms defined for prospective data collection (in the PRIMO protocol), specifically nurse and clinician questionnaires, which will not be available for the data collected retrospectively (in the PRIMO addendum).

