2.2.3 Safety populations

2.2.3.1 Safety Analysis Set (SAS)

The SAS will include all patients in the AES that had at least one robotic suture placed or attempted. Note that this definition will include all patients in the FAS as well as any other patients outside of this set (but in the All Enrolled Set) where robotic anastomosis is attempted but no robotic sutures placed. To classify as 'robotic anastomosis attempted' there will be a robotic time recorded on the CRF for at least one anastomosis.

As for the SAS, two sub-populations will be defined based on the SAS.

- The prospective patient sub-population
- The retrospective patient sub-population.

All summaries and analyses will be presented using all data combined and by sub-population.

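### A recorded robotic failure can leave the primary endpoint if its intended approach is entered as manual, and nothing in the SAP fixes or checks that entry

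*SAP*

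**What the plan says.** SAP 2.1.3.1 derives the primary endpoint from one form per anastomosis: "Form R or Anastomosis Data Form will be completed for each anastomosis". If the intended approach is entered as robotic, "then the anastomosis is included for this endpoint". The outcome then comes from the question on technical issues that forced an unplanned return to conventional suturing. A 'Yes' is a conversion: "If the response is 'yes' anastomosis will be classified as intra-operative change from robotic to manual" (= 'yes'). A 'No' with at least one robotic or robotic redo suture is no conversion. A blank answer is missing. For the other intent answer the rule is "If the planned approach was manual the result will be N/A", with no condition on robotic sutures, robotic time or the conversion answer.

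On how intent is captured, SAP 2.1.2 says "The intended operation (manual or robotic) is recorded together with the number of robotic sutures used and the number of manual sutures used". Neither document requires intent to be entered before the operation or before the first suture.

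SAP 1.1 adds retrospective patients through an addendum that "will collect as much data as possible (based on availability) using the same data collection process as for the prospective data collection". SAP 1.5 and 1.7 count these patients towards the 402.

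**The concern.** The denominator of a success proportion should not depend on the outcome. Here membership rests on a field that sits beside the outcome fields and is not locked. A case that was started with the robot and finished by hand could plausibly be entered as manual. A case completed with the robot gives little reason for that entry. Misclassification of this kind removes failures rather than successes, so the success rate rises.

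The clearest case is a record with intent 'manual' and 'Yes' to unplanned return to conventional suturing. The two answers conflict, because a return to conventional suturing presupposes a robotic start. As written, the derivation makes this record N/A, so the evidence of failure is lost. No consistency check is specified.

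At stake is the conclusion in SAP 1.7 that Symani is superior to manual methods, which is drawn if the lower 95% confidence limit exceeds 85%.

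**Working it through.** **Step 1: apply the rules of SAP 2.1.3.1 to each type of record.** Success is read as no conversion.

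| Intent answer | Conversion answer | Robotic sutures | Result |
|---|---|---|---|
| Robotic | No | at least 1 | success |
| Robotic | Yes | any | failure |
| Robotic | blank | any | missing |
| Manual | Yes | any | N/A |
| Manual | No | at least 1 | N/A |
| Manual | No | 0 | N/A |

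Rows 2 and 4 can describe the same surgical event and differ only in the intent entry. Row 2 counts against the device and row 4 does not count.

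**Step 2: the plan's own decision rule.** Inputs from SAP 1.7: reference 85%, alternative 89%, 402 anastomoses, stated power 85%, exact 95% limits. I take the limits as two-sided, which the SAP does not state.

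The exact lower limit for x successes in n is L(x, n), the 0.025 quantile of Beta(x, n − x + 1).

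- L(355, 402) = 84.8% and L(356, 402) = 85.03%, so the rule needs at least 356 successes (88.6%).
- P(X ≥ 356 | n = 402, p = 0.85) = 2.4%. This is the false-positive rate when no failure leaves.
- P(X ≥ 356 | n = 402, p = 0.89) = 64.9%. The stated 85% power is not reproduced. That is a separate matter and is not used below.

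**Step 3: one worked data set (assumed).** Take 402 robotic attempts with 342 successes and 60 failures, close to the 85% reference. Let k failures be entered as manual, so that n = 402 − k.

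| k | Share of failures | Observed rate | Lower limit | Rule met |
|---|---|---|---|---|
| 0 | 0% | 342/402 = 85.1% | 81.2% | no |
| 6 | 10% | 342/396 = 86.4% | 82.6% | no |
| 12 | 20% | 342/390 = 87.7% | 84.0% | no |
| 16 | 27% | 342/386 = 88.6% | just above 85.0% | yes |
| 17 | 28% | 342/385 = 88.8% | 85.3% | yes |

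**Step 4: false-positive rate over repeated studies.** Assume 402 independent attempts with a true success rate of 85%. Each failure leaves with probability q.

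- Probability that an attempt is retained: 0.85 + 0.15(1 − q).
- Apparent success rate: p′ = 0.85 / [0.85 + 0.15(1 − q)].
- For q = 0.10: 0.85 / 0.985 = 86.3%.
- False-positive rate: the sum over m of P(m retained) × P(Bin(m, p′) ≥ r(m)), where r(m) is the smallest count with L(r, m) above 85%.

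| q | p′ | False-positive rate |
|---|---|---|
| 0 | 85.0% | 2.4% |
| 0.05 | 85.6% | 4.4% |
| 0.10 | 86.3% | 9.4% |
| 0.20 | 87.6% | 29.0% |
| 0.30 | 89.0% | 60.8% |

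The documents give no value for q. The table shows how sensitive the rule is, not what will happen. SAP 2.4.4.1 fits a separate mixed model for each surgery type, and those limits would differ from these pooled exact ones.

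**The case against.** The main defence is that the restriction follows the endpoint. The protocol synopsis defines success as "the ability to complete the surgical task with Symani as intended by the surgeon". An anastomosis truly planned as manual is properly N/A, and a conversion entered with robotic intent stays in as a failure. This stands: the intended-robotic denominator is right in principle, and a failure leaves by this route only if its intent is entered as manual.

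Three stronger readings are tempting, and the documents do not support them.

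- **That every intent answer is given once the result is known.** SAP 2.1.2 says what is recorded together, not when each field is completed, and the case report forms are not among the documents. Entry after surgery is certain only for retrospective patients. For prospective patients the gap is that no rule fixes the time.
- **That the SAP contradicts itself because the safety set accepts robotic time as proof of an attempt.** SAP 2.2.3.1 does say "To classify as 'robotic anastomosis attempted' there will be a robotic time recorded on the CRF for at least one anastomosis". That set is defined by exposure and the primary endpoint by intent, so different criteria are not in themselves inconsistent.
- **That any robotic suture or robotic time should bring an anastomosis into the denominator.** Planned-manual hybrids with a few robotic sutures and a 'No' would then score as near-automatic successes and raise the rate. With an assumed 104 of them, 342/402 becomes 446/506 = 88.1%, with a lower limit just above 85.0%, so the rule would be met. Records with robotic time, no robotic sutures and a 'No' would enter without a class.

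It may also be said that a manual intent with a 'Yes' is a data-entry error that the form blocks or that cleaning would catch. That cannot be confirmed. SAP 2.4.3 lists and summarises the anastomosis data, so such records could be found, but no cross-check or rule for resolving them is specified.

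**Conclusion.** The point holds in a limited form. SAP 2.1.3.1 lets an intent answer that need not be fixed in advance, and that is entered after surgery for retrospective patients, remove an anastomosis whose own record shows a failed robotic attempt. The likely effect is an upward bias in the success rate.

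Its size is unknown. A reader might infer from the worked data set that superiority would be reached falsely. That needs about 27% of failures entered as manual, a share for which the documents give no basis; at 10% and 20% the rule is not met in that data set. What can be said is conditional: with independent anastomoses, a true rate of 85% and the exact-limit rule of SAP 1.7, loss of 5% of failures would raise the false-positive rate from 2.4% to 4.4%, and loss of 10% to 9.4%. Because the rule defines the primary denominator and the remedy is cheap, the gap should be closed before the analysis.

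**What to change.** In SAP 2.1.3.1:

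1. Keep the intended-robotic denominator, but include every anastomosis with a 'Yes' to the technical-issue question and score it as a failure, whatever the intent answer.
2. Query every manual-intent record that has a robotic time or robotic sutures, and report the number of such records by subpopulation (prospective, retrospective).
3. Do not add manual-intent records with a 'No' as successes in the primary analysis. Add a sensitivity analysis that counts manual-intent records with robotic evidence as failures.
4. For patients still to be operated on, record intent for each anastomosis before the first suture.

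Items 1 to 3 use fields already collected and cost some SAP wording, queries and programming. Item 4 needs an instruction to sites. The success rate may come out slightly lower. The sensitivity analysis is deliberately severe, because genuine planned hybrids will count as failures in it. These changes act within the FAS; patients with an attempt but no robotic suture placed are a separate question.
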